3.3 Secondary Study Endpoints

3.3.1 We will report the post-operative radiation dose coverage for the prostate, organs at risk, and targeted lesion for each case. The coverage for the brachytherapy implant will be reported for the V100, V150, and V200, i.e. volumes of the prostate receiving 100, 150, and 200% of the prescribed dose. The dose delivered to the targeted lesion or lesions will be reported as a V100, V150, V200 as well to evaluate the ability to target the dose escalation prospectively, though again is per routine and not as part of a therapeutic trial design at this time. Additionally, the D90, i.e. dose to 90 percent of the prostate volume will be reported. Doses to the bladder, rectum and urethra will also be calculated for evaluation in the study.

3.3.2 An additional secondary endpoint for the study will be to report the incidence of successful completion of the transperineal biopsy procedure using the Uronav system which is provided by Philips Medical as part of the support for this study. The Symphony biopsy system will be available in the operating room (OR) as a back-up to complete the biopsies if needed. It is, however, anticipated that the combined DynaCAD computer for processing the MR images and Uronav systems supplied for the study to integrate with our standard transperineal ultrasound system will be 100% successful in obtaining the required biopsies. We will also report on any unanticipated complications or infections. It is anticipated that the risk of infection should be substantially diminished by avoiding transrectal biopsies. However, the risk for prostate edema and urinary obstruction may be increased due to the additional transperineal needle placement as the biopsy will be followed by routine prostate brachytherapy. Patients may therefore be asked to maintain a Foley catheter overnight to allow edema to resolve, and avoid acute obstruction the following day. Assuming the Uronav system is capable of completing biopsies on all patients and no more than 1 patient acquires a post-operative infection this pilot study will be deemed a success, and further investigation may be warranted.

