4.2 Anticipated Number of Research Subjects

The pilot study is designed to include only 6 subjects for testing of feasibility to obtain transperineal tissues and report correlation to MRI image findings.

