5.1 Early Withdrawal of Subjects

5.1.1 Criteria for Removal from Study

Subjects may withdraw from the study at anytime prior to the procedure. They will be replaced by an additional subject to maintain 6 subjects in the cohort.

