10.2 Statistical Methods

Statistical analysis: The correlation of biopsy tissue histopathology with intraprostatic MRI findings will be estimated using binomial evaluation for True Positive, False Positive, True Negative, False Negative values to report Sensitivity, Specificity, and Positive as well as Negative Predictive value for parametric MRI findings relative to correlated histopathology. These data will be used for reporting the study results in regards to Specific aim 1, The infection rate and hospitalization rate within 30 days due to the procedure will be collected for expected acute events (AE's) and these data will be used for reporting the study results for specific aim 2 evaluation the transperineal use of Uronav to determine if the transperineal biopsy approach results in a reduced rate of infection or hospitalization compared to standard transrectal biopsies.

Any deviations from the previously described statistical plan will be described and justified in a protocol amendment.

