11.8 Stopping Rules

A stopping point will be enforced if 2 or more subjects develop infections requiring IV antibiotics or infections that require hospitalization if felt to be related to the procedure (i.e for example gram negative sepsis) within 30 days of the procedure.

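### The success limit of at most 1 infection in 6 men barely separates infection rates below about 25%, so meeting it cannot support a low or reduced infection risk, which Section 10.2 says the data will be used to judge

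*Combined protocol and SAP*

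**What the plan says.** Section 3.3.2 sets the plan's only overall success rule. It has two parts. The first is completion: "Assuming the Uronav system is capable of completing biopsies on all patients". The second is the infection limit: "no more than 1 patient acquires a post-operative infection this pilot study will be deemed a success, and further investigation may be warranted". The same paragraph expects that Uronav, with its companion planning computer, "will be 100% successful in obtaining the required biopsies", and says of infection: "It is anticipated that the risk of infection should be substantially diminished by avoiding transrectal biopsies".

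The denominator is fixed. Section 4.2 states: "The pilot study is designed to include only 6 subjects for testing of feasibility". Section 5.1.1 says of men who withdraw before the procedure: "They will be replaced by an additional subject to maintain 6 subjects in the cohort".

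Two other sections bear on how the infection count will be read. Section 10.2 says the 30-day infection and hospitalization data will be used to "determine if the transperineal biopsy approach results in a reduced rate of infection or hospitalization compared to standard transrectal biopsies". Section 9.2 lists procedure-related infection among the effectiveness measures and then says that, with so few subjects, no statistical analysis of effectiveness is anticipated.

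Section 11.8 gives the stopping rule: "A stopping point will be enforced if 2 or more subjects develop infections requiring IV antibiotics". It also counts infections that need hospitalization, and it is limited to procedure-related events within 30 days.

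**The concern.** The limit of 1 in 6 comes with no infection rate regarded as acceptable or unacceptable, no transrectal rate, no interval and no error probabilities. One infection in 6 is an observed rate of 16.7%, and it counts as success in a paragraph that anticipates a substantial fall in risk.

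The wording of the success rule is modest in itself, since it leads only to possible further investigation. The difficulty comes from Section 10.2, which assigns the same data to deciding whether infection is reduced relative to transrectal biopsy. Followed as written, the plan would let 0 or 1 infection in six uncontrolled men be reported as bearing on that question. What is at stake is the claim the trial may make about infection. Recruitment and treatment are not affected.

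**Working it through.** **Inputs.** n = 6 (Sections 4.2 and 5.1.1); pass if infections ≤ 1 and completions = 6 (Section 3.3.2). The documents give no infection rate for either route, so the true rate p is an assumption shown over a range. Infections are taken as independent between men.

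**The plan's own figure.** No operating characteristic is stated for this limit. The only power figure, 82% in Section 10.1, concerns lesion detection (22% against 11%, 84 sites, two-sided 0.05). A one-sample score test gives Φ[(√84 × 0.11 − 1.96 × √(0.11 × 0.89)) / √(0.22 × 0.78)] = Φ(0.953) = 0.830, close to the stated value. It says nothing about infection.

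**Chance of meeting the infection limit.** P(X ≤ 1) = (1 − p)^6 + 6p(1 − p)^5 = (1 − p)^5 (1 + 5p).

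| True rate p | Calculation | P(limit met) |
|---|---|---|
| 5% | 0.7738 × 1.25 | 0.967 |
| 10% | 0.5905 × 1.50 | 0.886 |
| 15% | 0.4437 × 1.75 | 0.776 |
| 20% | 0.3277 × 2.00 | 0.655 |
| 25% | 0.2373 × 2.25 | 0.534 |
| 40% | 0.0778 × 3.00 | 0.233 |
| 50% | 0.0313 × 3.50 | 0.109 |

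The probability equals 0.50 at p = 26.4% and falls to 0.05 only at p = 58.2%.

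**How much a pass discriminates.** A pass is 0.967 / 0.886 = 1.09 times as likely at a 5% rate as at 10%, and 0.967 / 0.655 = 1.48 times as likely as at 20%.

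**Exact (Clopper-Pearson) 95% intervals for results that pass.**
- 0/6: upper limit 1 − 0.025^(1/6) = 0.459, so 0% to 46%.
- 1/6: lower limit 1 − 0.975^(1/6) = 0.004; the upper limit solves (1 − p)^5 (1 + 5p) = 0.025, giving 0.641, so 0.4% to 64%.

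**Can the best result show a reduction?** Zero infections occur with probability 0.95^6 = 0.74 at a true rate of 5% and 0.90^6 = 0.53 at 10%. At one-sided 0.05, 0/6 is significantly low only against a fixed comparator rate above 1 − 0.05^(1/6) = 39%.

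**The full rule.** The table covers the infection part only. If each man's completion probability were 95% (assumed, and independent of infection), 6/6 would occur with probability 0.95^6 = 0.735. The whole rule would then be met with probability 0.735 × 0.967 = 0.71 at 5% infection and 0.735 × 0.886 = 0.65 at 10%. A result of 6/6 has an exact lower 95% limit of 0.025^(1/6) = 54%.

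**Infection definitions side by side.** Section 3.3.2 counts any post-operative infection, with no severity, time window or attribution. Section 10.3 counts infections needing IV antibiotics, or hospitalization, with no window or attribution. Section 11.8 counts infections needing IV antibiotics or hospitalization, if related to the procedure and within 30 days.

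**The case against.** The strongest defence is that this is a pilot and says so. Section 10.1 presents it as generating hypotheses, Sections 4.1 and 4.2 give feasibility as the goal, and Section 9.2 disclaims statistical analysis of effectiveness. The success sentence does not itself claim that infection is low or reduced, and any limit would be weak here: a zero-infection limit would still leave an upper bound of 46%. All of that stands. It is why the limit need not be replaced and why no larger trial is called for. It does not settle the matter, because Section 10.2 makes the inferential claim that Section 9.2 disclaims.

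Four stronger readings are tempting and should not be drawn.
- **That the limit cannot tell a low infection rate from a high one.** It can at the extremes: it is met 97% of the time at 5% and 11% at 50%.
- **That a pilot which escapes the stopping rule will nearly always pass.** The two rules count different events. As an assumed illustration, suppose 20% of men have any infection and one-fifth of those infections are severe, so 4% of men. The chance of not stopping is 0.96^5 × 1.20 = 0.978, and the chance of passing given no stop is 0.655 / 0.978 = 67%.
- **That the limit would usually be met even if infection were several times more common.** This depends on the baseline. Three times 10% is 30%, where it is met 42% of the time.
- **That success should rest on Uronav completion alone.** That would remove a safety condition the plan now has: 6/6 completions with three mild infections would count as success.

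**Conclusion.** The concern holds in this form: the limit of at most 1 infection in 6 is a coarse safety check that barely separates true rates below about 25% and usually fails only at very high ones. Results that pass leave upper 95% limits of 46% or 64%. Meeting it therefore supports neither the anticipated fall in infection risk nor the comparison with transrectal biopsy in Section 10.2. That comparison has no stated comparator rate, test or interval, and it conflicts with Section 9.2.

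The binomial figures rest on n = 6 and independence between men, and the rates shown are assumed because the documents give none. The limit is acceptable as a pilot go/no-go check; the fault lies in what a pass may be taken to show. With a pass leading only to possible further study, this should be corrected before results are reported, but it does not undermine the conduct of the pilot.

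**What to change.** Keep the existing success rule and describe it as a pilot feasibility and safety check. By protocol amendment:

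1. In Sections 3.3.2 and 10.2, add text such as: *The number of men with infection and the number with biopsies completed using Uronav will each be reported as x/6 with an exact (Clopper-Pearson) 95% confidence interval. Meeting the infection limit means only that no large safety signal was seen. It is not evidence that infection risk is low or reduced.*
2. In Section 10.2, replace the comparison with transrectal biopsy by descriptive reporting of infection and hospitalization within 30 days, which brings it into line with Section 9.2.
3. Reconcile the infection definitions in Sections 3.3.2, 10.3 and 11.8 for severity, time window and attribution. Which definition should apply is for the investigators to decide.

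The cost is a few sentences, with no added patients, procedures or data. The downside is a more modest claim about infection.

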3.4 Primary Safety Endpoints

The primary safety endpoint for the study will be the rate of infection or hospital admission within 30 days that are felt to be directly related to the procedure.

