Ohio) is used to align the MR image to the live ultrasound image to assist in needle placement and brachytherapy source delivery. During the procedure typically 20 to 35 needles are placed transperineally to deposit the brachytherapy sources per the computerized plan. Regions that are found to be suspicious for harboring cancer within the prostate volume are routinely planned to received a higher dose of radiation than the whole gland by placing additional radioactive sources at these locations at the time of the implant, however without a biopsy confirming the image findings it is unknown if these radiographic findings represent the biopsy proven disease site within the patients, or if these lesions may harbor higher grade disease or are false positive findings.

Hypothesis: Multiparametric MRI with histopathological correlation will improve the segmentation of the target volumes to treat sub-volumes of the prostate with focal dose escalation in low- and intermediate-risk patients beyond the use of imaging alone using standard T1 and T2 MRI and the addition of functional MRI sequences.

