2.0 Study Objectives

Specific Aim 1: Evaluate final pathology post-operatively for histopathology confirmation of multiparametric MRI targets detected during treatment planning. This will be accomplished by using transperineal biopsies obtained prior to interstitial brachytherapy during the procedure, while under anesthetic just prior to the placement of the brachytherapy needles and sources.

Specific Aim 2: Evaluate the ability of the Uronav system in a transperineal setting to guide biopsy needle placement using the electromagnetic guidance system and transperineal ultrasound probe stabilization device and stepper.

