3.2 Primary Study Endpoints

The primary endpoint will be to report correlation of biopsy tissue histopathology with intraprostatic MRI findings. A total of 12 to 15 tissue samples will be obtained from each subject using standard sextant biopsies in addition to targeted biopsies of intraprostatic MRI findings. Assuming 14 specimens are sent for histopathology analysis in 6 subjects we will use the 84 biopsy sites to report sensitivity and specificity for the MRI findings along with positive and negative predictive values.

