11.3 Expectedness

Adverse Events can be Expected or Unexpected.

An expected adverse event is an event previously known or anticipated to result from participation in the research study or any underlying disease, disorder, or condition of the subject. The event is usually listed in the Investigator Brochure, consent form or research protocol. Expected acute events in this study would be an infection requiring additional antibiotic treatment beyond the standard postoperative antibiotic given for the prostate seed implant, or readmission to the hospital for pain, infection, or obstruction as a result of the biopsies.

An unexpected adverse event is an adverse event not previously known or anticipated to result from the research study or any underlying disease, disorder, or condition of the subject.

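### The primary safety rate counts only events attributed to an undefined procedure, and a same-session biopsy and implant cannot give the biopsy rate that 10.2 compares with transrectal biopsy

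*Combined protocol and SAP*

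**What the plan says.** Section 3.4 defines the primary safety endpoint as "the rate of infection or hospital admission within 30 days that are felt to be directly related to the procedure". Section 10.2 repeats the condition: "The infection rate and hospitalization rate within 30 days due to the procedure will be collected". It then assigns these data to Specific Aim 2, to determine whether the transperineal approach has a lower infection or hospitalization rate than standard transrectal biopsy.

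The biopsies and the implant form one session. Section 2.0 has the biopsies taken "while under anesthetic just prior to the placement of the brachytherapy needles and sources". On the biopsy side, section 3.2 states: "A total of 12 to 15 tissue samples will be obtained from each subject". On the implant side, section 1.2 states: "During the procedure typically 20 to 35 needles are placed transperineally to deposit the brachytherapy sources per the computerized plan". Section 3.3.2 acknowledges that the two add up, linking a possible rise in edema and obstruction to the "additional transperineal needle placement as the biopsy will be followed by routine prostate brachytherapy".

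Section 4.2 plans six subjects. No implant-only group is described. The attribution scale in 11.4 has five levels, refers jointly to the study device or procedures, and sets no level at which an event becomes directly related.

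**The concern.** An infection or admission in the 30 days after the session has two candidate causes, minutes apart, through the same perineum. Whether it enters the primary safety numerator depends on a judgement of cause, and the plan does not say which intervention that judgement is about. Two careful analysts could build different numerators from the same six charts.

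What is at stake is the conclusion in 10.2. A rate that depends on an attribution the design cannot check, or that mixes biopsy and implant harm, would be presented as evidence about transperineal biopsy against transrectal biopsy.

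**Working it through.** The plan gives no target or reference figure for the safety endpoint. Its only power figure (82%, section 10.1) concerns lesion detection and plays no part here.

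**1. What the procedure refers to.**
- In 1.2, the sentence on needles refers back to the brachytherapy procedure.
- In 3.3.2, the phrase is qualified as the transperineal biopsy procedure.
- In 2.0 (Aim 1), the biopsies occur before brachytherapy within the procedure, which points to the whole session.
- In 3.4 and 10.2, the term is unqualified.

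The first three uses are clear in context. The two that define and analyse the endpoint are not.

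**2. What each reading gives.**
- *Biopsy only:* the numerator needs a split between biopsy-caused and implant-caused events. With one arm, one session and no implant-only comparator, nothing in the data informs that split.
- *Combined session:* the numerator is workable, but the rate includes implant harm and is not a biopsy rate.

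Neither reading supports the comparison in 10.2, for which the documents also give no transrectal reference rate.

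**3. Where a relatedness condition applies.**

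| Section | Use | Relatedness required? |
|---|---|---|
| 3.4 | Primary safety endpoint | Yes |
| 10.2 | Analysis | Yes |
| 7.1 | Follow-up data on infection and admission | Yes |
| 11.8 | Stopping rule | Yes |
| 3.3.2 | Success: at most 1 patient with post-operative infection | No |
| 10.3 | Stopping rule | No |
| 11.5 | Recording of adverse events | No |

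Sections 10.3 and 11.8 both stop at 2 or more subjects but differ in two ways. Only 11.8 requires relatedness. Section 11.8 limits qualifying hospitalization to infections, whereas 10.3 can be read to include hospitalization for any reason.

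**4. Size.** Reclassifying one event moves the rate by 1/6 = 16.7 percentage points. The exact two-sided 95% interval for 0 of 6 runs from 0 to 1 − 0.025^(1/6) = 45.9%; for 1 of 6 it runs from 0.4% to 64.1%. Even an unfiltered count is therefore very imprecise.

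**5. Illustration of the filter.** Let *t* be the true per-patient event rate and *q* the share of events judged related. Both are assumptions and neither is in the documents. With independent patients, the chance that two or more of six count is 1 − (1 − tq)^6 − 6tq(1 − tq)^5.

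| t | all count (q = 1) | half count (q = 0.5) |
|---|---|---|
| 10% | 11.4% | 3.3% |
| 20% | 34.5% | 11.4% |
| 30% | 58.0% | 22.4% |
| 40% | 76.7% | 34.5% |

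This shows how far attribution could change the count, not how often it will.

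**The case against.** The strongest reply is that the filter reaches little. Section 3.3.2 promises a report of any unanticipated complications or infections and judges success on post-operative infection without asking its cause. Section 10.3 stops without asking the cause. Section 11.5 has all adverse events after consent recorded and followed for 3 months, and 11.0 puts grade 2 and above into the database. An infection blamed on the implant would still be on file and would still count against success. Section 9.2 adds that no statistical analysis of effectiveness is expected with so few subjects. In a descriptive pilot of six, counting related events rather than all events is partly a design preference.

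Most of that stands. A reader might infer that biopsy harm will be attributed away; the documents do not show this, and the unfiltered provisions argue against it. Three other tempting inferences also fail:
- **Section 11.3 restricts the endpoint to biopsy-caused events.** It does not. It defines expected adverse events and does not use the term at issue. Its phrase "readmission to the hospital for pain, infection, or obstruction as a result of the biopsies" most naturally limits readmission only, not the infection clause before it.
- **Needle counts show how much risk belongs to the biopsy.** Nothing in the documents links the number of passes to infection or admission, and 6.1 allows a trocar that reduces placements.
- **The consultancies disclosed in section 16 show biased attribution.** They are stated to be within policy limits and are not evidence of that.

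The reply does not repair the primary rate, which remains filtered on an undefined term, or the use 10.2 makes of it. That the data are already recorded makes the remedy cheap rather than unnecessary.

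**Conclusion.** The point holds, limited to the primary safety rate and its interpretation. Sections 3.4 and 10.2 make the numerator depend on attribution to a procedure that neither defines, and the same-session, single-arm design cannot separate biopsy-caused from implant-caused events. The comparison with transrectal biopsy in 10.2 is unsupported on either reading of the term.

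Each event whose attribution is disputed is worth 16.7 percentage points. How many would be disputed cannot be derived from the documents, and the illustration rests on assumed rates. The conclusion assumes that the relatedness condition in 3.4 covers both infection and admission, which is the natural reading. It does not extend to a claim that events go unrecorded or that the success criterion is filtered.

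**What to change.** - **3.4 and 10.2:** report all infections and all hospital admissions within 30 days of the combined biopsy-plus-implant session, regardless of attribution. Show the attributed count beside this, by 11.4 category, separately for biopsy/device and for implant. Giving every category removes the need for a cut-off for directly related.
- **Label:** call the result a combined-session rate.
- **10.2:** remove the wording that uses the rate to determine a reduction compared with transrectal biopsy.
- **7.1:** align the follow-up wording so that capture of infection and admission is clearly all-cause.
- **10.3 and 11.8:** reconcile them on whether relatedness is required and whether non-infectious hospitalization counts.

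The cost is wording. Safety assessments are already planned for day 1 and visits 3 to 5, and 11.5 already requires all adverse events to be recorded, so no new visit is needed. The downside is that the reported rate may be somewhat higher because implant-related events are included; the attributed count beside it lets a reader see how much of it the investigators ascribe to each part.

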3.0 Study Design

3.1 General Design

This 1-year pilot study will include 6 patients with a clinical diagnosis of prostate cancer (clinical stage T2a or T1cN0M0), Gleason score ≤ 7 (4+3), with a PSA ≤ 15 ng/mL and routine pelvic screening with MRI of the prostate and pelvis for staging and treatment planning who have elected to undergo prostate brachytherapy as definitive treatment.

Only patients who have clinically detectable intraprostatic findings on the MRI will be eligible to participate, and will be screened from the routine population of patients undergoing prostate brachytherapy at University Hospitals.

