7.1 Follow-up Procedures

Patients will be followed for safety assessments at post-operative day 1, and at visits 3, 4, and 5. Data collection will include routine treatment data, assessment of urinary obstruction requiring Foley catheter placement as well as signs or symptoms of infection requiring additional antibiotics or hospital admission felt to be directly related to the procedure.

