10.3 Interim Analysis

Patients will be continuously monitored for safety and toxicity as we enroll up to 6 patients for the study. A stopping point will be enforced if 2 or more subjects develop infections requiring IV antibiotics or require hospitalization.

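### The two-subject stopping rule is not linked to open 30-day safety windows, so if implant dates cluster, most or all six men can be biopsied before a second event is known

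*Combined protocol and SAP*

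**What the plan says.** Section 3.4 defines the safety endpoint as "the rate of infection or hospital admission within 30 days that are felt to be directly related to the procedure".

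The stopping rule appears twice.
- Section 10.3: "A stopping point will be enforced if 2 or more subjects develop infections requiring IV antibiotics or require hospitalization". It gives no time window and no condition of relatedness.
- Section 11.8: "A stopping point will be enforced if 2 or more subjects develop infections requiring IV antibiotics or infections that require hospitalization", if judged related and "within 30 days of the procedure".

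On timing, section 10.3 says "Patients will be continuously monitored for safety and toxicity as we enroll up to 6 patients for the study". Section 7.1 says "Patients will be followed for safety assessments at post-operative day 1, and at visits 3, 4, and 5"; the section 7.0 table puts those visits at about 2 weeks, 1 month and 3 months. The only calendar limit is in section 3.1: "This 1-year pilot study will include 6 patients with a clinical diagnosis of prostate cancer". That is a study duration and sets no spacing. No section gives a minimum interval between biopsies, a pause, a cap on men with open windows, or a review before the next man.

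**The concern.** A rule that needs two events protects later men only if earlier men's events are known before the later men are biopsied. With six men there is little room for delay. Subjects come from men already scheduled for routine brachytherapy (3.1, 4.5), so biopsy dates follow the implant list and the plan does not control clustering.

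No other provision clearly fills the gap. Section 11.0 allows the evaluation to be paused, but for unanticipated events. Section 11.3 classes infection needing extra antibiotics, and readmission for pain, infection or obstruction, as expected. On its wording, the pause therefore does not reach the events that the stopping rule counts. Section 11.0 also has early-stopping endpoints reviewed, but gives no timing.

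The trial describes itself as non-therapeutic (4.1), and sections 3.3.2 and 11.1 say the added needles may raise the risk of edema and obstruction. The men at stake are those whose study biopsy would have been withheld had a second event been known in time.

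**Working it through.** **Inputs.** Six men (4.2: "The pilot study is designed to include only 6 subjects for testing of feasibility"); stop at two affected men (10.3, 11.8); 30-day window (3.4, 11.8); 1-year study (3.1); last visit at 3 months (7.0). The documents give no event rate p, accrual pattern or onset time. These are assumed and varied below. The plan states no operating characteristic for the stopping rule, so there is no figure of its own to reproduce.

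**Benchmark: every window closed before the next biopsy.** The rule stops before the sixth man if at least two of the first five have events:

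P = 1 − (1−p)^5 − 5p(1−p)^4

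- p = 10%: 1 − 0.590 − 0.328 = 8.1%
- p = 20%: 1 − 0.328 − 0.410 = 26.3%
- p = 30%: 1 − 0.168 − 0.360 = 47.2%

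This is a ceiling, because nobody is spared when the second event falls on the sixth man. At least two events in six occur with probability 11.4%, 34.5% and 58.0% at these rates. Perfect spacing thus spares at least one man in 0.081/0.114 = 71%, 0.263/0.345 = 76% and 0.472/0.580 = 81% of those cases.

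**As written: no spacing.** This was simulated with six entry dates uniform over the accrual period, onset uniform over days 0 to 30, and the rule acting as soon as the second event occurs. Probability of stopping before the sixth man:

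| Accrual period | p = 10% | p = 20% | p = 30% |
|---|---|---|---|
| 30 days | 2% | 6% | 13% |
| 90 days | 5% | 18% | 35% |
| 270 days | 7% | 24% | 43% |
| All windows closed | 8% | 26% | 47% |

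The 10% and 30% columns follow from P(at least 2 of 6) × (1 − share of those cases with all six already biopsied). At 30%, for example, this is 0.580 × (1 − 0.779) = 13% over 30 days and 0.580 × (1 − 0.258) = 43% over 270 days.

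**Expected men biopsied.** Over 270 days the figures are 5.86, 5.49 and 5.02 at 10%, 20% and 30%. With all windows closed they are 5.83, 5.41 and 4.87. The differences are 0.03, 0.08 and 0.15 of a man.

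**How likely is clustering?** Taking 3 months of follow-up from the year leaves about 270 days for accrual. Evenly spread biopsies would be 270/6 = 45 to 270/5 = 54 days apart, longer than the window. With random entry over T days and w = 30/T, all six fall within 30 days with probability 6w^5 − 5w^6, about 0.002% for T = 365. At least one gap under 30 days has probability 1 − (1 − 150/T)^6, which is 96% for T = 365 and 99% for T = 270. Some overlap of windows is therefore near certain under random entry, but complete overlap needs deliberate or list-driven grouping of implant dates.

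**The case against.** The strongest reply is that monitoring is continuous, so the rule acts on the second known event and need not wait for day 30 or a scheduled visit. Infections needing IV antibiotics and hospital admissions come to notice quickly. Even with all six men entered within 30 days, onset within 7 days (assumed) leaves about a 21% chance of stopping before the sixth man at a 20% event rate, and 38% at 30%. Over a 9-month accrual the plan as written comes within 2 to 4 percentage points of the ceiling at those rates. Section 3.3.2 expects less infection than with the transrectal route, and at a 10% event rate any gain is about one point over 270 days. The system is described as 510K approved (6.1), and no dose is escalated between men.

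All of this stands as a limit on size. A reader might infer that the rule is void, with its chance of acting falling from 26% or 47% to zero. The documents do not support that: zero needs both extreme clustering and late onset, while the plan has continuous monitoring and a year to run. What the reply leaves open is that monitoring reveals an event but obliges nobody to wait, and no text prevents clustering.

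**Conclusion.** The gap is real and modest under ordinary accrual. At assumed event rates of 20% and 30%, the plan as written loses about 2 and 4 percentage points in the chance of stopping before the sixth man if entry spreads over 9 months. At 20% it loses about 8 points if accrual takes 90 days (18% against 26%) and about 20 points if it takes 30 days (6% against 26%). These figures rest on assumed event rates, random entry dates and onset uniform over 30 days. Earlier onset shrinks the loss and later onset enlarges it. It would be wrong to conclude that the rule cannot act, or that spacing would protect every man. The supported conclusion is that the rule's protection depends on the implant schedule, which the plan leaves uncontrolled. The remedy is cheap enough that the plan should be changed.

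**What to change.** 1. **Reconcile 10.3 and 11.8 first.** They differ on the 30-day window, on relatedness, and on whether any hospitalization counts or only hospitalization for infection. Until one definition is settled, it is unclear which event a hold should follow.
2. **Add an enrolment hold to both sections, tied to the reconciled event.** After the first counted event, no new study biopsy is done until every man already biopsied has completed the 30-day window. Tying it to counted events keeps minor adverse events from freezing enrolment.
3. **State how biopsies are paced before any event.** Give either a minimum interval or a maximum number of men with open windows. The hold alone cannot help men biopsied before the first event surfaces. The choice of interval or number is the sponsor's.

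**Cost.** A few sentences, and about one to two weeks of extra accrual on average at 9-month accrual for the hold; any interval adds to this according to its length. A man whose implant date falls in a hold has his routine implant without the study biopsy and is not enrolled.
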